(i) Fidelity assessed according to a fidelity checklist (developed in collaboration with the delivery team, prior to the internal pilot – see later in Process Evaluation) (green= ≥ 80 of sessions meet criteria; amber=50-79%; red=<50%);

(ii) Adherence: session attendance (green= $\geq 75\%$ of families attend at least the first 8 of the 10 sessions; amber= 50-74%; red=<50%).

Outcomes

(i) Data completeness for the Strengths and Difficulties Questionnaire (SDQ) parent reported young person externalising problems score at baseline: green= $\geq 75\%$; amber=50-74%; red=<50%.

The final progression criterion will be an assessment to confirm that the support in the intervention arm is sufficiently different to the control arm. This will be an assessment based primarily on a SAU survey.

Information from the SAU survey will be examined for any overlap with the content of the TEEN TRIPLE P intervention.

Design

A two-arm cluster (with families as the clusters) randomised efficacy RCT of Standard Teen Triple P (TEEN TRIPLE P) plus SAU vs. SAU alone, running over 40 months, involving parents and foster carers of young people aged 11-15 years on the edge-of-care. There will be a 6- and 12-month follow-ups, and a process evaluation and internal pilot.

Procedure

Parents and foster carers identified by case-holding social workers and edge-of-care teams across six local authorities (Cambridgeshire, Peterborough, Birmingham, London Borough Merton, Gloucestershire, and Wirral). Participants (primary parents/carers) will be screened by case-holding social workers and edge of care teams to check initial eligibility. Those who are likely to be eligible will be invited to take part in the trial.

All participants who agree to participate and for whom consent has been given will be screened to ensure they meet the eligibility criteria. Consent from those with parental responsibility is required, and young person assent when under 16 years of age – for research participation by young people. If the local authority has parental responsibility, then the social worker would consent to the inclusion of the young person on behalf of the local authority.

Baseline assessments will be completed prior to randomisation. Families randomised to the intervention arm will receive TEEN TRIPLE P as well as existing edge-of-care services (SAU), and those randomised to the control arm will receive SAU alone.

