Qualitative	Interviews (semi-structured)	At least 35 parents/carers, at least 10 adolescents, and at least 15 practitioners, in both the TEEN TRIPLE P trial arms	Framework thematic analysis	RQ6 and 8	Perceptions of stakeholders are a key component to assess change processes
-------------	------------------------------	--	-----------------------------	-----------	--

Safety reporting

Serious adverse events and adverse events will be assessed by the Trial Steering Committee and reported to the Research Ethics Committee for consideration as required.

The site Principal Investigator (PI) is responsible for ensuring that all site staff involved in this trial are familiar with the content of this section.

All SAEs must be reported immediately (and within 24 hours of knowledge of the event) by the PI at the participating site to the Trial team unless the SAE is specified as not requiring immediate reporting. The University of Warwick SOP will be followed and all SAEs/AEs will be reviewed by the PI at site. The safeguarding policy of each Local Authority site will be followed.

Definitions

This trial will collect GCP SAEs and trial-specific SAEs and AEs.

SAEs and AEs need to be reported for all trial participants, therefore parent(s) and the young person participating in the trial.

Table 4. SAE definitions

Term	Definition
Serious Adverse Event (SAE) (GCP)	
Any adverse event that -
 
 • Results in death • Is life-threatening* • Required hospitalisation or prolongation of existing hospitalisation** • Other medically important condition***

***Note:** The term 'life-threatening' in the definition of serious refers to an event in which the trial participant was at risk of death at the time of the event or it is suspected that used or continued used of the product would result in the subjects death; it does not refer to an event which hypothetically might have caused death if it were more severe.

**** Note:** Hospitalisation is defined as an inpatient admission, regardless of the length of stay, even if the hospitalisation is a precautionary measure for continued observation. Pre-planned hospitalisation e.g., for pre-existing conditions which have not worsened, or elective procedures, does not constitute an SAE.

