***** Note:** other events that may not result in death, are not life-threatening, or do not require hospitalisation, may be considered as an SAE when, based upon appropriate judgement, the event may jeopardise the participant and may require intervention to prevent one of the outcomes listed above

Trial specific SAE reporting requirements

In addition to the SAE reporting requirements above, for the purposes of this trial the following events will also be considered SAEs and must be captured on the SAE form and reported to the University of Warwick CI(s) and Trial manager with 24 hours of knowledge of the event:

- Detention within hospital using the Mental Health Act
- Increasing suicidal ideation and/or plans or actual attempts to harm oneself with associated suicidal intent. Practitioners will report any incidence of this occurring.

The following will be considered AEs:

- Deliberate self-harm which is not life-threatening nor associated with suicidality as judged by the practitioner.
- A deterioration in mental state defined as increased anxiety, low mood, aggression, or new evidence of thought disorder and/or perceptual disturbances as judged by the practitioner.
- Disclosure of a history of physical and/or sexual abuse and/or criminal exploitation.
- Imprisonment.
- Removal from the family home.
- Safeguarding risk to the young person has increased during their participation in the trial to such an extent that the LA have had to initiate care proceedings.

Causality

Causal relationship will be assessed for the Teen Triple P parenting intervention. The Principal Investigator (or another delegated qualified person from the trial team) will assess each SAE to determine the causal relationship and the Chief Investigator (or another appropriately

qualified member of the Trial Management Group) can also provide this assessment where necessary:

Table 5 Causality in SAEs

Relationship	Description	Reasonable possibility that the SAE may have been caused by the intervention?
Unrelated	There is no evidence of any causal relationship with the intervention	No
Unlikely	There is little evidence to suggest there is a causal relationship with the intervention. There is another reasonable explanation for the event.	No
Possible	There is some evidence to suggest a causal relationship with the intervention. However, the influence of other factors may have contributed to the event.	Yes

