Probable	There is evidence to suggest a causal relationship and the influence of other factors is unlikely.	Yes
Definite	There is clear evidence to suggest a causal relationship and other possible contributing factors can be ruled out.	

The causality assessment given by the Principal Investigator at Local Authority site (or delegate) cannot be downgraded by the Chief Investigators (or delegate), and in the case of disagreement both opinions will be provided.

Expectedness

The Chief Investigator (or another delegated appropriately qualified individual) will assess each SAE to perform the assessment of expectedness.

Expected events (AE) will be listed here:

Increased expression of emotion (e.g., crying) during sessions with a practitioner.

This event does not need to be reported as an AE.

Reporting procedures

Participating Site Responsibilities

The Local Authority site PI should sign and date the SAE CRF to acknowledge that he/she has performed the seriousness and causality assessments. Investigators should also locally report SAEs in accordance with local practice.

A completed SAE form for all events requiring immediate reporting should be submitted via email to the University of Warwick Chief Investigators and Trial Manager within 24 hours of knowledge of the event. A separate form must be used to report each event, irrespective of whether or not the events had the same date of onset.

The participant will be identified only by Participant identification number, partial date of birth (mm/yy) and initials. The participant's name should not be used on any correspondence.

It is also required that sites respond to and clarify any queries raised on any reported SAEs and report any additional information as and when it becomes available through to the resolution of the event. Additionally, the University of Warwick evaluation team may request additional information relating to any SAEs and the site should provide as much information as is available to them in order to resolve these queries.

Serious Adverse Event (SAE) email address

[contact]

Serious adverse events should be reported throughout the treatment period up to 28 days after the participant receives the intervention.

An SAE form is not considered as complete unless the following details are provided:

- Full participant trial number

- An Adverse Event

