- A completed assessment of the seriousness, and causality as performed by the PI (or another appropriately qualified person registered on the delegation log).

If any of these details are missing, the site will be contacted and the information must be provided by the site to the University of Warwick team within 24 hours.

All other AEs should be reported on the CRF.

Expected adverse events will be assessed by the Trial Steering Committee and reported to the Research Ethics Committee for consideration as required.

The University of Warwick evaluation team responsibilities

Following the initial report, all SAEs should be followed up to resolution wherever possible, and further information may be requested. Follow up information must be provided on a new SAE form.

The University of Warwick evaluation team should continue reporting SAEs until 28 days after the participant receives the last part of the intervention. Once an SAE is received by the University of Warwick evaluation team, it will be evaluated by the Chief Investigator(s) (or their delegate) for an assessment of expectedness.

Related and unexpected Serious Adverse Events (SAEs) will be submitted to the Sponsor and the Research Ethics Committee. These should be sent within 15 days of the CI becoming aware of the event.

Urgent Safety Measures (USMs)

An urgent safety measure is an action that the Sponsor, Chief Investigator or site Principal Investigator may carry out in order to protect the subjects of a trial against any immediate hazard to their health or safety.

Any urgent safety measure relating to this trial must be notified to the Research Ethics Committee immediately by telephone, and in any event within 3 days in writing, that such a measure has been taken. USMs reported to the University of Warwick evaluation team will be reported to the Research Ethics Committee

Cost data reporting and collecting

We propose to collect data to enable us to estimate the delivery costs of TEEN TRIPLE P, as follows:

- 1) Personnel for the implementation of the programme. Collected from the delivery team including the number of TEEN TRIPLE P sessions delivered per parent and the number of person days per parent.
- 2) Programme costs. Collected by the delivery team including costs of travel per family.
- 3) Facilities, equipment and materials. Collected from the delivery team and LAs, including costs to local authority delivery teams of any support materials needed for the intervention.

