Exploratory mediation analyses may also be carried out to examine variables at 6 months that may mediate intervention effects between baseline and 12-month follow-up. Mediation analyses will use the same two-level model setup as in the main analysis, but will have the following additional steps:

- Initial model, outcome regressed on all independent variables except mediator (same as main analysis).

$$Y_i = \beta_0 + \beta_1 SDQ_{BLi} + \beta_2 local_authority_i + \beta_3 TX_i + \varepsilon_i,$$

$$\varepsilon_i \sim N(0, \sigma^2)$$

- Second, the same model is fitted but the dependent measure is exchanged for the mediator.

$$M_i = \beta_0 + \beta_1 SDQ_{BLi} + \beta_2 local_authority_i + \beta_3 TX_i + \varepsilon_i,$$

$$\varepsilon_i \sim N(0, \sigma^2)$$

- Finally, the first model is refitted but with the inclusion of the mediator as an additional independent variable.

$$Y_i = \beta_0 + \beta_1 SDQ_{BLi} + \beta_2 local_authority_i + \beta_3 TX_i + \beta_4 M_i + \varepsilon_i,$$

$$\varepsilon_i \sim N(0, \sigma^2)$$

Using these model parameter estimates and the 'mediate' function from the R package 'mediation', the average causal mediation effects can be estimated following the procedure from Imai et al. (2010). The mediation analyses will use the bootstrapped procedure as this method has no distributional assumptions on the indirect effect and is generally more robust (Bollen & Stine, 1990).

Harms

The number (and percentage) of patients experiencing each AE/SAE will be presented for each treatment arm categorised by severity. For each patient, only the maximum severity experienced of each type of AE will be displayed. The number (and percentage) of occurrences of each AE/SAE will also be presented for each treatment arm. No formal statistical testing will be undertaken.

Statistical software

All statistical analyses will use R version 4.1.2 (2021-11-01) with additional packages: tidyverse, pwr, VGAM, lme4, lmerTest, performance, mice, psych, ivreg, and ivpack.

References

Joshua D. Angrist & Guido W. Imbens (1995) Two-Stage Least Squares Estimation of Average Causal Effects in Models with Variable Treatment Intensity, *Journal of the American Statistical Association*, 90:430, 431-442, 10.1080/01621459.1995.10476535

Barnett, A.G., & Dobson, A.J. (2008). *An Introduction to Generalized Linear Models* (3rd ed.). Chapman and Hall/CRC. <https://doi.org/10.1201/9781315182780>

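### The SAE reporting window is tied to receiving Teen Triple P, so families on support as usual have no defined window and the by-arm harms table has no assured common observation period

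*Protocol*

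**What the plan says.** **Who is covered.** Protocol, Safety reporting, Definitions: "SAEs and AEs need to be reported for all trial participants, therefore parent(s) and the young person participating in the trial". Both arms are in scope.

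**When serious events are reported.** Under Participating Site Responsibilities: "Serious adverse events should be reported throughout the treatment period up to 28 days after the participant receives the intervention". Under the evaluation team's responsibilities: "The University of Warwick evaluation team should continue reporting SAEs until 28 days after the participant receives the last part of the intervention". The two end-points are worded differently, but both depend on receipt of the intervention.

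**When other events are reported.** Non-serious events go on the CRF, with no general start or end date in either arm. One listed event, safeguarding risk that leads to care proceedings, is worded by reference to the person's time in the trial.

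**What control families receive.** Protocol, Design, Procedure: "those randomised to the control arm will receive SAU alone".

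**Who identifies events.** Under the trial-specific reporting requirements, practitioners report increasing suicidal ideation (an SAE). Self-harm without suicidality and deterioration in mental state (both AEs) are classified "as judged by the practitioner".

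**What is tabulated.** SAP, Harms: "The number (and percentage) of patients experiencing each AE/SAE will be presented for each treatment arm categorised by severity". Also: "The number (and percentage) of occurrences of each AE/SAE will also be presented for each treatment arm". No formal test is planned. No window or person-time denominator is given.

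**The concern.** A table of counts and percentages by arm can be read as a comparison only if both arms were observed for the same time. Here the only stated rule for serious events cannot be applied to half of the randomised families. Each site would have to improvise, and sites may improvise differently.

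The rule is also loose within the intervention arm. Sessions can be deferred, so the end date differs by family. A family that stops early would have an earlier end date, and one that never starts would have none. The window thus depends on allocation and on behaviour after randomisation.

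Monitoring adverse events is a stated objective, and no separate data monitoring committee is planned; the Trial Steering Committee is expected to take that role. Whoever reads the harms table would be unable to tell a true difference from one produced by the reporting rule.

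**Working it through.** The plan states no SAE rate and no window length in days, so there is no figure to reproduce. The check has two parts.

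**1. Can the rule be applied to each arm?**

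| Item | Teen Triple P + SAU | SAU alone |
|---|---|---|
| In scope for AE/SAE reporting | Yes | Yes |
| SAE start | Not dated (treatment period) | None |
| SAE end | 28 days after the intervention, or its last part | None |
| Window for non-serious AEs | None, one event excepted | None, one event excepted |
| Tabulated in the SAP | Yes | Yes |

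The protocol's schedule of procedures has no AE/SAE row, so no stated assessment at 6 or 12 months supplies a common period instead.

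**2. How much could it matter? (illustration only)**

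Inputs:
- Treatment of 10 sessions over 10 weeks (SAP summary table).
- 28 days added (Protocol, Safety reporting).
- Randomisation ends 30/09/2024 and delivery ends 20/01/2025 (Protocol, Timeline).
- Follow-up at 6 and 12 months, taken as 182 and 365 days.
- SAU reporting to either of those points is my assumption; the documents do not state it.

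Intervention window:
- Short case, weekly delivery counted from the first session: 10 × 7 + 28 = 98 days.
- Long case, latest timeline dates counted from randomisation: 112 + 28 = 140 days.

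Ratio of observation time = intervention days ÷ SAU days:

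| Assumed SAU period | 98 days | 140 days |
|---|---|---|
| 182 days | 98/182 = 0.54 | 140/182 = 0.77 |
| 365 days | 98/365 = 0.27 | 140/365 = 0.38 |

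If sites instead applied a nominal treatment period plus 28 days to SAU families, the ratio would be about 1.

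To express this as counts, assume the same constant hazard in both arms, with annual risk r: h = −ln(1 − r)/365, and P(at least one event in d days) = 1 − exp(−h·d). With 206 parents/carers per arm (young people are also covered, so this is a partial count), the expected numbers with an event are:

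| Assumed r | 98 days | 140 days | 182 days | 365 days |
|---|---|---|---|---|
| 5% | 2.8 | 4.0 | 5.2 | 10.3 |
| 10% | 5.7 | 8.2 | 10.5 | 20.6 |
| 20% | 12.0 | 16.9 | 21.7 | 41.2 |

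At 10%, for example, identical true risk could appear as 5.7 against 20.6. Under-recording in SAU families, for want of a window, would push the comparison the other way.

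**The case against.** Several counter-arguments have force.

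- **Undefined is not unequal.** A reader might infer that the plan observes the arms for different lengths of time, so that the table is confounded. The documents do not say so. They give no SAU period, and sites could apply matching periods. What stands is that nothing assures equality.
- **The 28-day rule covers serious events only.** It should not be read as governing self-harm or mental-state deterioration, which are listed as AEs. For those the gap is different: neither arm has a stated window.
- **This is not the trial's only evidence on safety.** Out-of-home placement, Kessler 6, SWEMWBS and the SDQ are collected on the same schedule in both arms, and the researchers collecting data are to be blind. Worsening could show there. The harms table is the planned comparison of AEs and SAEs as such.
- **Practitioner reporting may not be one-sided.** The Risks section (Contamination) says that different practitioners will serve each condition, so SAU families have practitioners too. SAU contact frequency is not stated, so unequal detection is possible but of unknown size. Death, hospitalisation, Mental Health Act detention and imprisonment do not rest on practitioner judgement.
- **The stakes are limited.** The objective concerns events related to Teen Triple P, causality is assessed for the intervention, the table is descriptive, and the Trial Steering Committee assesses events. The protocol also invokes a University SOP, not seen here, which might set a window.

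These points reduce the severity. They do not supply an SAE end date for SAU families, and an SOP that did so would still have to be reconciled with the protocol's text.

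**Conclusion.** The point holds in a limited form. The protocol requires event reporting in both arms but defines the SAE window by receipt of an intervention that one arm never gets. It sets no general window for other AEs. The by-arm table therefore rests on periods that are undefined for SAU and not assured to match.

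The ratios of 0.54 to 0.77 and 0.27 to 0.38 show what could happen if SAU reporting ran to 6 or 12 months. They are not estimates of bias in this trial. A reader might go further and conclude that the apparent ratio of events could be unbounded because sites would record nothing for SAU families; that would contradict the requirement to report events for all participants. The direction of any distortion cannot be known in advance.

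The primary outcome analysis is unaffected. The plan should be changed because the gap is avoidable and cheap to close.

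**What to change.** In the protocol's Safety reporting section, reconcile the all-participants requirement with the two 28-day statements. Replace them with one AE/SAE reporting window that applies identically to both arms and is anchored to randomisation. Its length is for the sponsor to set.

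In the SAP's Harms section, state that window and base the numbers and percentages by arm on events falling within it.

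The cost is a small protocol amendment, a matching SAP edit and some additional SAE forms. A common window does not by itself equalise detection, so the report should say who identified the events. Having blinded researchers ask every family about events is an option rather than part of this fix: disclosures would trigger 24-hour reporting and site safeguarding procedures, and the conversation could unblind the researcher.

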Sessions 4 – 9 are focussed on the actual intervention, whereby each session of active training (sessions 4, 6, and 8) are followed by practice sessions (sessions 5, 7, and 9). Sessions 4-5 cover promoting appropriate behaviour, sessions 6-7 are for managing problematic behaviour, and sessions 8-9 are on dealing with risky behaviour.

Session 10 the final session covers additional skills to facilitate generalisation and maintenance of treatment gains and intervention review and closure.

Parents receive a Standard Teen Triple P Family Workbook to support them in using the strategies and processes taught during the Standard Teen Programme. The Family Workbook covers each individual session including information, practice tasks, and space for taking notes/recording progress to encourage implementation of Triple P in the family. Parents retain the workbook following completion of the individual sessions.

Location: Standard Teen Triple P is delivered in the family home. There is flexibility where this is not feasible for delivery to occur in other locations, for example Local Authority or community premises where there is a private space to meet. There is also the option to deliver the programme remotely via videoconferencing where suitable.

Frequency: Standard Teen Triple P is delivered on a weekly basis over 10 weeks. There is flexibility if parents are unable to attend a session - for example due to illness or planned vacations - for practitioners to defer a session to accommodate such family life events.

Dosage: Standard Teen Triple P is a ten-session programme. Attendance at all sessions is preferable. It is practice as usual to offer alternative times/dates if a session is missed due to unforeseen circumstances.

All the parenting strategies within the Standard Teen Programme are taught by the close of Session 8 (of 10) so there is a case that completion of sessions 1-8 would be considered dose sufficient.

Implementation and practitioner training – Standard Teen Triple P

The trial will be supported by TPUK's Implementation Consultant for Research, using the Triple P Implementation Framework (McWilliam, Brown, Sanders & Jones, 2016). This framework is used to guide the implementation of Triple P through every stage, to make sure the programme is as effective as possible for families, and realistic for practitioners to deliver. This helps to sustain the programme and to get the most out of it for families in the community.

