Participants have the right to withdraw consent for participation in any aspect of the trial at any time. The participants care will not be affected at any time by declining to participate or withdrawing from the trial because they will still receive support services as usual. If a participant initially consents but subsequently withdraws from the trial, clear distinction will be made as to what aspect of the trial the participant is withdrawing from. These aspects will be:

- Withdrawal from intervention (TEEN TRIPLE P only).
- Partial withdrawal from future follow-up data collection (e.g., some questionnaires, interviews).
- Withdrawal from previously collected data, prior to data analysis.

Participants who consent and subsequently withdraw should complete the trial withdrawal form or the withdrawal form should be completed on the participant's behalf by the site staff/trial team based on information provided by the participant. This withdrawal form should be sent to the Trial email address. Any queries relating to potential withdrawal of a participant should be forwarded to the Trial Manager, [name].

Participant retention

Participants who do not complete the 6-month follow-up data collection will be considered lost to follow-up. The trial team will monitor retention throughout the trial. To minimise loss to follow-up participants (both CYP and parent/guardian) will be (i) offered shopping vouchers for taking part in this trial, contingent upon questionnaire completion at each time-point, which will be stepped to encourage completion at the follow-up timepoints (baseline=£10, 6-months=£20, 12-months=£25). CYP and parent/guardian will also be offered £20 shopping vouchers for participating in an interview, and (ii) sending CYP and their families 'thank you' cards following each contact.

Some participants may have difficulties with reading and writing. We will make materials (including trial materials such as PIS where possible) available in alternative formats (e.g., audio file, video) and provide a choice of data completion methods (see earlier). The materials will be written in easy to read, lay language. Participants will be given the choice of how to complete the follow-up questionnaires (with a Research Assistant face-to face, over the telephone, or via videoconferencing, or directly in the secure bespoke online database).

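### SAE reporting ends 28 days after the intervention is received, so control families have no defined end date and the harms table by arm may compare unequal observation time

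*Protocol*

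**What the plan says.** Four places bear on the point.

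- Protocol, Safety reporting, Definitions, on who is covered: "SAEs and AEs need to be reported for all trial participants, therefore parent(s) and the young person participating in the trial". No period is given.
- Protocol, Participating Site Responsibilities, on how long sites report: "Serious adverse events should be reported throughout the treatment period up to 28 days after the participant receives the intervention".
- Protocol, responsibilities of the University of Warwick evaluation team: the team "should continue reporting SAEs until 28 days after the participant receives the last part of the intervention".
- SAP, Harms, on presentation: participants with each event are counted by arm and severity, and "The number (and percentage) of occurrences of each AE/SAE will also be presented for each treatment arm". No formal test is planned. The section states no observation window and no person-time.

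The Protocol's Procedure section says that "those randomised to the control arm will receive SAU alone". Its Withdrawal section lets a family leave the intervention only. The table of data collection timepoints has no row for AEs or SAEs.

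**The concern.** A percentage by arm is interpretable only if both arms are observed for the same period, or if the table shows how the periods differ. Here the duty to report covers both arms, but the rule for when it ends can be applied only to people who received the programme. A site with a control family has to decide for itself when SAE reporting stops, and sites may decide differently.

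Within the intervention arm, one of the two rules makes the window depend on sessions attended, which is behaviour after randomisation. The harms table could therefore show a difference between arms that is only a difference in time observed, or could hide a real one. The listed SAEs include detention under the Mental Health Act and increasing suicidal ideation, and the Trial Steering Committee is expected to take the role of a data monitoring committee. Events not reported at the time may be hard to recover later.

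**Working it through.** The plan gives no figure for observation time, so there is none to reproduce. The check sets the rules side by side, works out the window lengths they imply, and illustrates the effect on the percentages.

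**Step 1. Apply the rules to each kind of family.**

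| Family | Must be reported? | Site rule | Evaluation team rule |
|---|---|---|---|
| Completes 10 sessions | Yes | Treatment period plus 28 days | Session 10 plus 28 days |
| Stops after session 2 | Yes | Depends on the meaning of treatment period | Session 2 plus 28 days |
| Allocated, never starts | Yes | No date of receipt | No last part received |
| Control | Yes | No date of receipt | No last part received |

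The last two rows have a duty to report but no defined end date. Both rules concern SAEs only. For other AEs no general period is stated in either arm.

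**Step 2. Window length for families who start.** The Protocol's Frequency paragraph says "Standard Teen Triple P is delivered on a weekly basis over 10 weeks". If session s falls 7(s − 1) days after session 1, the evaluation team rule closes at

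L(s) = 7(s − 1) + 28 days after session 1.

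- s = 1: 0 + 28 = 28 days
- s = 2: 7 + 28 = 35 days (5 weeks)
- s = 5: 28 + 28 = 56 days
- s = 8: 49 + 28 = 77 days
- s = 10: 63 + 28 = 91 days (13 weeks)

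If the site rule's treatment period means the scheduled 10 weeks whatever the attendance, the length is 70 + 28 = 98 days for every family that starts. For a family stopping after session 2, the two rules could then differ by 98 − 35 = 63 days.

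**Step 3. Effect of unequal windows when true risk is equal.** The documents give no SAE rate, so assume an annual risk a of 5%, 10% or 20%, constant over time and the same in both arms. The share with an event in d days is P = 1 − (1 − a)^(d/365).

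| Window | a = 5% | a = 10% | a = 20% |
|---|---|---|---|
| 35 days | 0.5% | 1.0% | 2.1% |
| 91 days | 1.3% | 2.6% | 5.4% |
| 98 days | 1.4% | 2.8% | 5.8% |
| 182 days | 2.5% | 5.1% | 10.5% |
| 365 days | 5.0% | 10.0% | 20.0% |

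If controls were reported for a full year and intervention families for 98 days, the control percentage would be about 3.5 times as high with no true difference (for example 10.0 / 2.8 = 3.6). In person-time from a 13-week window, the ratio would be 26 / 13 = 2 with controls followed to 6 months and 52 / 13 = 4 with controls followed to 12 months. No passage says that controls are reported for either period. These figures show sensitivity to the reading; they do not predict a result.

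**The case against.** The other side has several good points.

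- *Controls are covered.* A reader might infer that control SAEs go unreported and the control column would be empty. The Definitions text rules that out, since it covers all participants. What is missing is the end date.
- *Early leavers may not be worse off.* The SAP summary gives treatment duration as ten sessions over ten weeks, and the schedule has a treatment phase column. On that reading the site rule does not shorten with attendance. The early-leaver point therefore rests on the evaluation team rule alone. Even on that reading, a control family has no first session to start the clock, and the site rule still ends by reference to receiving the intervention.
- *Stopping because of deterioration.* A reader might infer that the worst cases are lost. The documents give no evidence of this, and an SAE before stopping or within 28 days after it is still inside the window.
- *Later harms are not all lost.* One listed AE is tied to participation in the trial, not to sessions. Out-of-home placement, which overlaps the AE of removal from the home, is recorded at both follow-ups in both arms. The 28-day limit applies to SAEs only.
- *Thirteen weeks is not a ceiling.* It runs from session 1, not randomisation, and sessions may be deferred. The timeline ends randomisation on 30/09/2024 and delivery on 20/01/2025, which is 112 days. Adding 28 gives 140 days, or 20 of 26 weeks (77%) for a family randomised on the last day.
- *The objective is narrow.* Secondary objective 4 in the Protocol concerns events related to Teen Triple P, and a window tied to the intervention suits that aim. The reporting duty and the SAP table are wider: they cover all participants and both arms.
- *Low stakes for inference.* Harms are descriptive, the trial is rated low risk, and a University SOP that may set a period is cited but not reproduced.

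These points limit the size and reach of the problem. None of them supplies an SAE end date for control families or for those who never start.

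**Conclusion.** The point holds in limited form. The Protocol requires SAE reporting for everyone, but both stated end dates depend on receiving the intervention, so control families and allocated families who never start have no defined end date. Under the evaluation team rule, though not necessarily the site rule, early leavers have a shorter window: about 5 weeks against 13 from session 1, assuming weekly sessions without deferral. The SAP percentages by arm may therefore reflect different observation time.

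A reader might go on to infer that the table will understate harm in the intervention arm by a factor of 2 or 4. The documents do not support that, because the factor and its direction depend on how sites fill the gap. The event rates used above are assumptions. The primary analysis and sample size are unaffected, and no harms test is planned. The matter is worth an amendment but is not critical to the trial's main conclusion.

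**What to change.** Reconcile the Definitions, site and evaluation team texts into one reporting window counted from randomisation, identical in both arms and independent of sessions attended. The trial team should set its length; the documents give no basis for prescribing one here. Apply it to SAEs and other AEs, and add an AE/SAE row to the Protocol's table of data collection timepoints. In the SAP Harms section, state that events are counted within that window and give person-time by arm, so that withdrawal and loss to follow-up are visible.

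With a common window, equal true rates give equal expected percentages under equal follow-up, whatever length is chosen. The cost is a Protocol and SAP amendment and some extra event reporting by sites, mainly for control families and after sessions have ended.
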